5.1 Sample Size Justification

A 3 + 3 dose-escalation scheme will be conducted, with 3 to 6 DLT-evaluable patients evaluated at each dose level. It is expected that as many as 30 patients will be enrolled in the dose-escalation part of this study.

Once the MTD/R2PD has been established, the following 2 expansion cohorts will be treated at the MTD or RP2D:

1. Proteasome inhibitor-naïve expansion cohort including approximately 8 organ response-evaluable patients. There will be approximately 83% probability of observing at least 2 patients with organ responses among 8 patients based on the binomial probability calculation if the overall organ response rate is 35% for this population. Approximately 10 patients will be enrolled to obtain 8 response-evaluable patients.
2. Proteasome inhibitor-exposed expansion cohort including approximately 14 organ response-evaluable patients. There will be approximately 80% probability of observing at least 2 patients with organ responses among 14 patients based on the binomial probability calculation if the overall organ response rate is 20% for this population. Approximately 16 patients will be enrolled to obtain 14 organ response-evaluable patients.

Proteasome inhibitor-naïve patients are the patients who have not received any prior bortezomib contained therapy and the proteasome inhibitor-exposed patients are the patients who received at least one prior bortezomib contained therapy. Because approximately 6 patients in the dose-escalation part of the study will be included in the expansion cohorts, approximately 20 patients will be enrolled in the expansion part of this study. Please note that this is only for sample size justification, and the sponsor can stop the study enrollment for expansion cohorts at any time if deemed appropriate.

Overall, as many as 50 patients will be enrolled in this study.

5.2 Randomization and Stratification

No randomization or stratification will be performed in this study. Patients will be enrolled in successive dose cohorts during dose escalation. For the MTD disease expansion cohorts, patients will be enrolled in 1 of 2 expansion cohorts based on whether they have received a proteasome inhibitor-containing therapy.

5.3 Unblinding

As this is an open-label study; no unblinding methodology is required.

MLN9708
Study C16007 Statistical Analysis Plan

5.4 Data Handling

5.4.1 Methods for Handling Missing Data

Decisions regarding eligibility for this study may be made using local laboratory determinations in the dose-escalation segment of this study. For dosing decisions, local hematology and chemistry laboratory results may be used.

All available efficacy and safety data will be included in data listings. For summary tables, laboratory test results from the central laboratory will be used when they are available. Laboratory test results from local laboratories will be used only when no central laboratory test results exist at the same scheduled sample collection time point and when the local laboratory results support an adverse event (AE), dose modification, or other medical decision.

5.4.2 Definition of Baseline Values

Unless otherwise specified, the baseline value is defined as the value collected at the time closest to, but before, the start of study drug administration.

5.4.3 Windowing of Visits

All data will be categorized based on the scheduled visit at which they were collected. These visit designators are predefined values that appear as part of the visit tab in the electronic case report form (eCRF).

Refer to protocol Section 7.4.14 for details about the PK and pharmacodynamic sample collection windows.

5.4.4 Justification of Pooling

All data from all sites will be pooled. Study center or treatment-by-center interaction will not be included in any statistical analysis.

Due to the use of modified accelerated titration design for dose escalation, at a minimum, 1 patient will be dosed at any given dose level. Data may be pooled across dose levels for summary purposes. When appropriate, data will be summarized for patients at each dose level and pooled dose levels during dose escalation, patients at each expansion cohort (including the patients at MTD during dose escalation), all patients enrolled at the MTD dose level, and all patients overall.

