6.4 Dose-escalation Rules

The dose intervals will follow the 3+3 traditional escalation rules, starting with the treatment of 3 patients at a planned dose level:

1. If 0 of 3 patients experiences DLT, dose-escalation will proceed to the next higher dose level at which 3 patients will be enrolled.
2. If 1 of 3 patients experiences DLT, 3 more patients will be enrolled at that same dose level.
3. Escalation will continue if 1 of 6 patients experiences DLT.
4. If 2 or more patients in any dose level experience DLT, dosing will stop, and the previous dose level may be considered the MTD or an alternative dose between this dose level and the previous dose level might be further explored.

Figure 6-1 Dose-escalation Algorithm

Planned Dose Levels of MLN9708

The estimated safe starting dose of MLN9708 was selected from the dose-escalation portion of the C16004 study, a phase 1 study of weekly dosing in patients with relapsed and refractory multiple myeloma. The starting dose for Study C16007 was to be either at least 1 dose level below the MTD from Study C16004 if it had been determined and, if not, then a dose level completed without DLTs. The starting dose of 4.0 mg (flat dose) is dose level 2 as seen in [Table 6-1](#). This dose represents a dose completed without reported DLTs in Study C16004 since the MTD has not been determined in that study.

A population PK analysis was performed for MLN9708 to assess the feasibility of switching from BSA-based dosing to flat dosing. A population PK model was built using nonlinear mixed effects modeling in NONMEM VII software compiled with the Intel Fortran 9.2 compiler. Data from both the twice weekly and once weekly IV dosing regimens were used in the analysis (N = 42). Population PK analysis showed that MLN9708 PK can be well described by a 3-compartment model with linear elimination. Race, sex, BSA, and/or body

weight do not appear to significantly affect clearance (CL) and volume of distribution (V_1) in the central compartment. Clearance and volume of distribution in the central compartment are the PK parameters that will affect AUC and C_{max} , respectively. CL and V_1 are primary parameters that are independent of the route of administration of drug. Therefore, BSA is not expected to affect C_{max} or AUC after oral dosing, and thus flat dosing is appropriate for both oral and IV routes of administration.

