The RP2D estimation will be established following evaluation of the available data which will include, but is not limited to, toxicity characterization (Grade 3/4 AEs, SAEs, all grades peripheral neuropathy, and treatment discontinuation) with efficacy (hematologic and organ responses) also taken into consideration. The RP2D will require first cycle DLTs in not more than 0 in 3 or 1 in 6 DLT-evaluable patients enrolled in a single cohort. For the purpose of the RP2D estimation, Cycle 1 data from 6 evaluable patients will be used in addition to the available clinical data supporting tolerance over multiple treatment cycles. AEs that meet DLT criteria in Cycle 2 and beyond will not necessarily influence dose-escalation, but will be considered when determining the RP2D. Toxicities leading to dose modification in Cycle 2 and beyond will not necessarily influence dose-escalation, but will be considered when determining the RP2D.

Once the MTD/RP2D has been established, 2 expansion cohorts of patients with relapsed or refractory amyloidosis, including approximately 10 proteasome inhibitor-naïve patients and approximately 16 proteasome inhibitor-exposed patients, will be treated at the MTD/RP2D to more fully characterize the safety, tolerability, and efficacy of MLN9708, and the PK and pharmacodynamics of MLN9708 in this patient population. As many as 30 patients will be enrolled in the dose-escalation portion of the study, and as many as 20 additional patients (26 in total, including 6 patients from the dose-escalation portion) will be enrolled in the expansion cohorts.

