8. STATISTICAL AND QUANTITATIVE ANALYSES

8.1 Statistical Methods

8.1.1 Determination of Sample Size

A 3 + 3 dose-escalation scheme will be conducted, with 3 to 6 DLT-evaluable patients evaluated at each dose level. It is expected that as many as 30 patients will be enrolled in the dose-escalation part of this study.

Once the MTD/R2PD has been established, the following 2 expansion cohorts will be treated at the MTD or RP2D.

1. Proteasome inhibitor-naive expansion cohort including approximately 8 organ response-evaluable patients. There will be approximately 83% probability of observing at least 2 patients with organ responses among 8 patients based on the binomial probability calculation if the overall organ response rate is 35% for this population. Approximately 10 patients will be enrolled to obtain 8 response-evaluable patients.
2. Proteasome inhibitor-exposed expansion cohort including approximately 14 organ response-evaluable patients. There will be approximately 80% probability of observing at least 2 patients with organ responses among 14 patients based on the binomial probability calculation if the overall organ response rate is 20% for this population. Approximately 16 patients will be enrolled to obtain 14 organ response-evaluable patients.

Because approximately 6 patients in the dose-escalation part of the study will be included in the expansion cohorts, approximately 20 patients will be enrolled in the expansion part of this study.

Overall, as many as 50 patients will be enrolled in this study.

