1.1 Study Design

This is an open-label, multicenter, phase 1, dose-escalation study of MLN9708 in adult patients with previously treated systemic light-chain (AL) amyloidosis. A 3 + 3 dose-escalation scheme will be implemented. Patients will receive escalating doses of MLN9708 orally (PO) on Days 1, 8, and 15 in a 28-day cycle in the absence of disease progression (PD) or unacceptable toxicity. If there is no hematologic response (complete response [CR], very good partial response [VGPR], or partial response [PR]) after completion of 3 cycles of single-agent MLN9708, dexamethasone will be added on Days 1 to 4 of every cycle (Days 1-4 every 28 days) beginning with Cycle 4. The patient's response status will be reassessed after 3 additional cycles; if there is no hematologic response at that time, the patient will be removed from treatment and followed for survival.

Once the maximum tolerated dose (MTD)/recommended phase 2 dose (RP2D) has been established, 2 expansion cohorts of patients with relapsed or refractory amyloidosis, including approximately 10 proteasome inhibitor-naïve patients and approximately 16 proteasome inhibitor-exposed patients, will be treated at the MTD/RP2D to more fully characterize the safety, tolerability, and efficacy of MLN9708, quality of life (QOL), and the pharmacokinetics (PK) and pharmacodynamics of MLN9708 in this patient population.

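### SAP 5.4.4 pools escalation patients into the expansion cohorts by MTD rather than by the dose those cohorts receive, and it names an escalation design this trial does not use

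*SAP*

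**What the plan says.** On the escalation design, SAP 5.4.4 states: "Due to the use of modified accelerated titration design for dose escalation, at a minimum, 1 patient will be dosed at any given dose level". Permission to pool across dose levels follows directly. SAP 1.1 says instead "A 3 + 3 dose-escalation scheme will be implemented", and SAP 5.1 says "A 3 + 3 dose-escalation scheme will be conducted, with 3 to 6 DLT-evaluable patients evaluated at each dose level". Protocol 6.4 agrees with these two: "The dose intervals will follow the 3+3 traditional escalation rules, starting with the treatment of 3 patients at a planned dose level". SAP Section 6, which lists departures from the protocol, mentions no change of escalation design.

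On who is pooled, the summary groups in SAP 5.4.4 include "patients at each expansion cohort (including the patients at MTD during dose escalation" (the bracket closes there), followed by a group of all patients enrolled at the MTD level. Protocol 8.1.1 and SAP 5.1 describe the expansion dose differently: "the following 2 expansion cohorts will be treated at the MTD or RP2D". Protocol 6.4 bases the RP2D on more than Cycle 1 toxicity: "AEs that meet DLT criteria in Cycle 2 and beyond will not necessarily influence dose-escalation, but will be considered when determining the RP2D". Efficacy is also taken into account there. Protocol 4.1 lets escalation stop either at the MTD or at a maximum planned dose found to be safe.

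**The concern.** There are two problems in one paragraph, and they differ in weight.

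The first is a plain contradiction. The only reason the SAP gives for pooling dose levels is a design with possible single-patient levels, and no other section describes such a design.

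The second is the pooling key. The plan lets the expansion dose differ from the MTD, but SAP 5.4.4 identifies the escalation patients who join the expansion summaries by the MTD alone. Safety, the MTD and the RP2D are the primary objectives, and the expansion summaries are meant to characterize safety and activity at the dose taken forward. If the two doses differ, those summaries would combine patients who started at different doses, and would leave out patients who belong in them.

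**Working it through.** **1. Design statements side by side.**
- SAP 5.4.4: modified accelerated titration, at least 1 patient per level.
- SAP 1.1 and protocol 4.1: 3 + 3.
- SAP 5.1 and protocol 8.1.1: 3 + 3, with 3 to 6 DLT-evaluable patients per level.
- Protocol 6.4: 3 patients at a new level, and 3 more if 1 of the 3 has a DLT.

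Protocol 4.1 and the notes to Table 6-1 allow more cautious escalation, alternative dosing and enlargement of a level. None of these creates single-patient levels.

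**2. The plan's own figures (SAP 5.1, protocol 8.1.1).**
- Enrolment: 10 + 16 = 26; 26 − 6 = 20 new expansion patients; 30 + 20 = 50 overall. All reproduce.
- Naïve cohort, at least 2 responses in 8 at a rate of 35%: 1 − 0.65^8 − 8 × 0.35 × 0.65^7 = 0.831, stated as 83%.
- Exposed cohort, at least 2 responses in 14 at a rate of 20%: 1 − 0.80^14 − 14 × 0.20 × 0.80^13 = 0.802, stated as 80%.

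None of these depends on the accelerated-titration sentence, so replacing it moves no sample-size figure.

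**3. The pooling rule read literally, in the three cases the protocol allows.**

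| Case | Escalation patients added by SAP 5.4.4 | Result |
|---|---|---|
| Expansion dose equals the MTD | Those at the expansion dose | As intended |
| Expansion at an RP2D below the MTD | Those at the MTD | Two starting doses mixed; escalation patients at the expansion dose omitted |
| Escalation ends at a maximum planned dose, no MTD | None | Expansion summaries lose the patients who were to be carried over |

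In the second case the separate MTD-level group would hold escalation patients only. In the third it would be empty.

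**4. Size in the second case.** Let m be the number of escalation patients at the MTD, with 20 new expansion patients. The share of the combined expansion summaries at a different starting dose is m / (20 + m).
- m = 3: 3 / 23 = 13%.
- m = 6: 6 / 26 = 23%.

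The range for m is an assumption. Under protocol 6.4 the level below one with 2 or more DLTs may be taken as the MTD, and that level may have had only 3 patients. The plan's figure of about 6 counts patients carried into expansion on the expectation that they share its dose; it does not count patients at a higher MTD. The share within a single cohort depends on how the carried-over patients split by prior proteasome-inhibitor exposure, which the documents do not state.

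**The case against.** The best defence is that MTD is used as shorthand for the expansion dose. Protocol 4.1 and 6.4 and SAP 1.1 write MTD/RP2D as one dose, SAP 5.2 speaks of MTD expansion cohorts, and protocol 7.3 gives every expansion patient the same initial dose. Read that way, SAP 5.4.4 means escalation patients at the expansion dose and nothing goes wrong. This is probably what was meant, and it limits the point to a conditional one. It does not remove the point: protocol 8.1.1 and SAP 5.1 write MTD *or* RP2D, the protocol gives the two different bases, and an MTD may never be identified. A programmer should not have to infer which patients belong in a column.

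The accelerated-titration sentence also looks like text carried over from another plan. SAP 5.10.2 refers to a tumor pharmacodynamic expansion cohort that this protocol does not have, and SAP 5.4.3 cites a protocol section number that does not match where the PK sampling windows now stand (7.5.13). This is inference, but it makes a deliberate change of design unlikely.

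A reader might infer that pooling on this mistaken basis hides the dose-toxicity pattern. The documents do not support that. SAP 5.4.4 itself plans summaries at each dose level alongside pooled ones, softened only by a when-appropriate qualifier. SAP Section 5 analyses patients at their assigned level, SAP 5.7.2 reports exposure and dose modifications by level, and SAP 5.10.1.5 lists DLTs by level. The MTD follows from the protocol's escalation rules in the DLT-evaluable population, not from pooled tables. Comparing a minimum of 3 patients with a minimum of 1 likewise measures no effect on any analysis. Protocol 8.1.6 separately permits combining doses other than the expansion dose for efficacy, so pooling does not rest on this sentence alone.

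**Conclusion.** The point holds in two parts. The accelerated-titration sentence in SAP 5.4.4 certainly contradicts the rest of the SAP and the protocol, but correcting it changes no result. The MTD-based pooling rule is the substantive part, and it is conditional. If the expansion dose is the MTD, it has no effect. If it is not, the rule mixes two starting doses, or selects no escalation patients when there is no MTD, and it omits escalation patients treated at the expansion dose.

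The illustrative share is 13% to 23% of the combined expansion summaries, assuming 20 new expansion patients and 3 to 6 escalation patients at the MTD. The upper figure should not be read as fixed by the plan. Nor should a reader conclude that the trial ran a different escalation design or that the sample size is wrong: the documents support neither. Severity is minor to moderate.

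**What to change.** In SAP 5.4.4:
- Replace the accelerated-titration sentence with the 3 + 3 description already in SAP 5.1, so that the section agrees with protocol 6.4.
- Replace both MTD-based group definitions with *patients assigned in dose escalation to the same dose as the expansion cohorts*. This matches protocol 8.1.6, which separates patients by the expansion dose, and it works whether that dose is the MTD, a different RP2D or a maximum planned dose.
- State that pooled columns are additional to the columns for each assigned dose level and never replace them.

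The cost is SAP wording and table headers. No patients, data or escalation rules change.

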5.5 Patient Disposition

A tabulation of patient disposition data will include a summary of the number of patients in the Safety, PK, and Pharmacodynamic analysis population, the DLT-Evaluable population, the Response-Evaluable population, and the primary reasons for study discontinuation.

Patients will be considered to have completed the study if they:

- Have received at least 6 cycles of treatment, or
- Experience PD after completing at least 28 days of Cycle 1

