4.3 Duration of Study

The duration of enrollment will be approximately 24 months.

Patients who have a response to treatment may remain on treatment for a maximum of 12 cycles or until the occurrence of PD or unacceptable toxicity, whichever occurs first. Patients who stop treatment for any reason other than disease progression will continue in PFS follow-up and be seen every 6 weeks until documented disease progression. After disease progression, all patients will continue to the OS follow-up part of the study and will be contacted every 12 weeks.

Delayed treatment-related AEs will be followed for 30 days after last dose of study drug or until initiation of subsequent antineoplastic therapy. The analyses for the clinical study report will be conducted after 75% of patients have PD or 12 months after last patient is enrolled, whichever occurs first in the study.

It is anticipated that this study will last for approximately 84 months. The duration of follow-up for overall survival will be 60 months after the last patient enters the study. Treatment may be continued in this study or in a MLN9708 rollover study, if and when such a study is made available, upon request by the investigator and agreement by the project clinician.

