7.7 Completion of Treatment

Patients will be considered to have completed study treatment if they meet any of the following criteria:

- Have received at least 6 cycles of treatment
- PD after at least 28 days of Cycle 1

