7.8 Completion of Study

Patients will be considered to have completed the study if they complete treatment according to the criteria outlined in Section 7.7 and complete 6 months of follow up (after the last dose of MLN9708).

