5. STATISTICAL METHODOLOGY

Analyses will be primarily descriptive in nature. No formal statistical tests will be performed. Summary tabulations will be presented that display the number of observations, mean, standard deviation, median, minimum, and maximum for continuous variables, and the number and percentage (calculated using nonmissing values) per category for categorical data, unless specified otherwise.

Patients will be analyzed at the dose level to which they were originally assigned, including those who receive subsequent treatment at a lower dose level.

The analyses for the clinical study report (CSR) will be conducted after 75% of patients have PD or 12 months after last patient is enrolled, whichever occurs first in the study. At that time, all relevant data will be queried and cleaned; a database snapshot will be taken and used for the CSR. Additional follow-up treatment data will be entered into the database through study termination. Analyses may be updated based on additional information. An addendum to the CSR may be written if warranted based on these analyses. If deemed appropriate, however, the sponsor may decide to perform the analyses for CSR at the end of the study (EOS), which is approximately 2 years after the last patient is enrolled.

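### SAP 5.5 counts patients as study completers on the protocol's treatment-completion criteria alone, and SAP 5 still describes an end of study that the current protocol has moved

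*SAP*

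**What the plan says.** **Completion.** Protocol 7.7 concerns treatment: "Patients will be considered to have completed study treatment if they meet any of the following criteria". The criteria are receipt of six or more cycles, or progression once the 28 days of Cycle 1 have passed. Protocol 7.8 concerns the study. It asks that 7.7 be met and that the patient also "complete 6 months of follow up (after the last dose of MLN9708".

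SAP 5.5 begins "Patients will be considered to have completed the study if they" and gives six or more cycles as the first criterion and "Experience PD after completing at least 28 days of Cycle 1" as the second. It sets no follow-up condition. The same section promises a tabulation of the main reasons for leaving the study. SAP 6, which lists departures from the protocol, mentions the PK and pharmacodynamic populations and the vital-organ terminology, but not this.

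**End of study.** SAP 5 allows the sponsor to run the report analyses at "the end of the study (EOS), which is approximately 2 years after the last patient is enrolled". Protocol 4.3 states: "The duration of follow-up for overall survival will be 60 months after the last patient enters the study". The Protocol Summary and Section 7.5.17 also give 60 months, and the Summary and 4.3 put total duration at about 84 months. SAP 5.8.1 uses end of study as one limit of its second time frame for response rates and responder status; the other limit is the start of alternative antineoplastic therapy.

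**The concern.** A disposition table is where a reader looks first to see how many patients were followed as planned. Under SAP 5.5, a patient who finishes Cycle 6 and is lost the following week is a study completer. Protocol 7.8 would not count that patient, and Protocol 7.10 lists loss to follow-up, withdrawal and death as reasons for leaving the study. A non-responder taken off treatment after Cycle 6 meets the SAP rule at once, although Protocol 4.1 sends that patient into survival follow-up. What is at stake is the accuracy of one reported count, under a label that the protocol defines differently.

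The end-of-study description raises a consistency question. The two documents give different dates for the same milestone, and SAP 5.8.1 relies on that milestone.

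**Working it through.** **1. The completion rules as sets.** Let A be the patients who meet Protocol 7.7, and B those with six months of follow-up after the last dose.

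| Rule | Source | Patients counted |
|---|---|---|
| Completed treatment | Protocol 7.7 | A |
| Completed study | Protocol 7.8 | A and B |
| Completed study | SAP 5.5 | A |

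Every patient in *A and B* is in A, so the SAP count is never below the protocol count. The excess is the number in A but not in B. It is zero only if every treatment completer also finishes the six months.

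**2. Earliest time at which each rule can be met.** Inputs are a 28-day cycle with doses on Days 1, 8 and 15 (Protocol 4.1), no delays, and six months taken as about 183 days.

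- Progression route, all Cycle 1 doses taken and none later: SAP, about Day 29. Protocol, last dose on Day 15, so 15 + 183 = Day 198.
- Six-cycle route, stopping after Cycle 6: the last dose is on Day 5 × 28 + 15 = 155 and the cycle ends on Day 6 × 28 = 168. SAP, during or at the end of Cycle 6. Protocol, 155 + 183 = Day 338.

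These are earliest cases. A patient treated for 12 cycles meets the SAP rule at Cycle 6 and the protocol rule six months after a much later dose, so there is no single interval between the two.

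**3. Size of the over-count.** The documents give no rate of death, withdrawal or loss in the six months after the last dose. For illustration only, assume 40 treatment completers:

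| Assumed share without six months of follow-up | SAP count | Protocol count | Excess |
|---|---|---|---|
| 0% | 40 | 40 | 0 |
| 10% | 40 | 36 | 4 |
| 20% | 40 | 32 | 8 |
| 30% | 40 | 28 | 12 |

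**4. End of study.** Protocol 4.3 gives about 24 months of enrollment. Adding 60 months of survival follow-up gives 24 + 60 = 84 months, which reproduces the protocol's stated duration. The SAP's description implies 24 + 24 = 48 months. The difference is 84 − 48 = 36 months.

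**5. Where each item is used.**

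- The completion label: the disposition summary in SAP 5.5 only. The populations in SAP 2, the endpoints and censoring rules in SAP 5.8.1 and the intervals in SAP 5.8.2 do not refer to it.
- End of study: the optional report timing in SAP 5 and the second time frame in SAP 5.8.1. The default report trigger is progression in 75% of patients or 12 months after the last enrollment, whichever is first, and does not depend on it.

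**The case against.** The strongest reply is that nothing estimated depends on the completion label. The analysis is descriptive, the time-to-event data are listed by patient under SAP 5.8.2, and follow-up is better judged from those listings. That stands, and it limits the point to a mislabelled count.

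It can also be said that the Protocol 7.8 rule is itself a weak index of survival follow-up. A patient lost in month 7 after the last dose is a completer despite the 60-month plan, while one who dies in month 4 with full survival data is not. That is true. It is a reason not to over-read the corrected row, but not a reason to report a different rule under the protocol's name.

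On end of study, the SAP is dated November 2012, and the Amendment 6 summary shows that two years was once the protocol's figure. The SAP therefore appears simply not to have been updated. SAP 5 also provides for data entry through study termination, updated analyses and a report addendum. This explains the mismatch and limits its effect, but the current texts still disagree.

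A reader might infer three stronger claims that the documents do not support:

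- *Later survival and response data are lost, amounting to 36 of 60 months.* The 60 months is survival follow-up. Protocol 7.5.17 stops response assessment at progression or new therapy. SAP 5.8.1 censors survival at the date last known alive at the time of analysis. The survival endpoint in Protocol 3.2 is the one-year probability, and one year has elapsed for every patient by 12 months after the last enrollment.
- *Completers disappear from the table of reasons for leaving the study.* SAP 5.5 does not say that they are excluded from it.
- *Every patient is counted complete six months early.* Step 2 shows that the interval varies, and SAP 5.5 assigns no completion date.

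**Conclusion.** The point holds as a definitional error in SAP 5.5, undeclared in SAP 6. Its direction is certain: the reported number of study completers is at least the protocol-defined number. Its size cannot be computed from the documents and may be zero; the counts in the working rest on assumed loss rates. No efficacy estimate, population or censoring rule is affected.

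The end-of-study mismatch is a separate and smaller point. It is 36 months on paper. In practice it matters only if the sponsor takes up the end-of-study report, or if a patient still free of progression and of new therapy has a first or better response more than about 24 months after the last enrollment. Such a patient is possible, because Protocol 7.5.10 provides for treatment beyond 24 cycles (24 × 28 = 672 days, about 22 months). The documents do not say how many to expect.

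Both corrections should be made. The first changes a reported figure, and the second removes a conflict over a date that SAP 5.8.1 uses.

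**What to change.** **SAP 5.5.** Relabel the two existing criteria as *completed treatment*, citing Protocol 7.7. Add a row for *completed study*: Protocol 7.7 met, plus six months of follow-up after the last dose as in 7.8. Derive it from the last-dose and follow-up dates, and state how many days count as six months. Because a death within that period fails 7.8 as written, show such deaths separately from withdrawals and losses.

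**SAP 5.** Align the end-of-study description with the current protocol, at 60 months after the last patient enters, so that the time frames in 5.8.1 use the same milestone. If the sponsor wants to keep about two years for the response time frame, declare and justify that in SAP 6.

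**Cost.** SAP wording, one derived variable and an extra disposition row. The protocol already schedules PFS visits every 6 weeks and survival contacts every 12 weeks, so no new assessments are needed. Protocol 7.9 says that the reason for stopping study drug is recorded on the eCRF, but 7.10 does not say so for reasons for leaving the study. Check that before promising reasons for both rows. The study-completion percentage may fall.
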